[Additional visits]	Full IHV01/A244	x	x	x.x	x	x.x	x	x.x	x	x.x	x	x.x
	Fractional IHV01/A244	x	x	x.x	x	x.x	x	x.x	x	x.x	x	x.x
	Full IHV01/A244 + ALFQ	x	x	x.x	x	x.x	x	x.x	x	x.x	x	x.x
	Fractional IHV01/A244 + ALFQ	x	x	x.x	x	x.x	x	x.x	x	x.x	x	x.x
	Placebo	x	x	x.x	x	x.x	x	x.x	x	x.x	x	x.x
Max Severity Post Baseline	Full IHV01/A244	x	x	x.x	x	x.x	x	x.x	x	x.x	x	x.x
	Fractional IHV01/A244	x	x	x.x	x	x.x	x	x.x	x	x.x	x	x.x
	Full IHV01/A244 + ALFQ	x	x	x.x	x	x.x	x	x.x	x	x.x	x	x.x
	Fractional IHV01/A244 + ALFQ	x	x	x.x	x	x.x	x	x.x	x	x.x	x	x.x
	Placebo	x	x	x.x	x	x.x	x	x.x	x	x.x	x	x.x
Note: The “Max Post Baseline” rows indicate the maximum severity experienced by each participant at any time point post baseline, including unscheduled assessments. N = Number of participants in the Safety Population with available samples; n = Number of participants reporting each severity												

Table 28: Laboratory Summary Statistics by Visit and Vaccination Group – [Parameter]

Time Point	Vaccination Group	N	Mean	Standard Deviation	Median	Min, Max
Baseline (Day 0)	Full IHV01/A244	x	xx.x	xx.x	xx.x	xx.x, xx.x
	Fractional IHV01/A244	x	xx.x	xx.x	xx.x	xx.x, xx.x
	Full IHV01/A244 + ALFQ	x	xx.x	xx.x	xx.x	xx.x, xx.x
	Fractional IHV01/A244 + ALFQ	x	xx.x	xx.x	xx.x	xx.x, xx.x
	Placebo	x	xx.x	xx.x	xx.x	xx.x, xx.x
[Additional visits]	Full IHV01/A244	x	xx.x	xx.x	xx.x	xx.x, xx.x
	Fractional IHV01/A244	x	xx.x	xx.x	xx.x	xx.x, xx.x
	Full IHV01/A244 + ALFQ	x	xx.x	xx.x	xx.x	xx.x, xx.x
	Fractional IHV01/A244 + ALFQ	x	xx.x	xx.x	xx.x	xx.x, xx.x
	Placebo	x	xx.x	xx.x	xx.x	xx.x, xx.x
[Additional visits, Fold Change from Baseline]	Full IHV01/A244	x	xx.x	xx.x	xx.x	xx.x, xx.x
	Fractional IHV01/A244	x	xx.x	xx.x	xx.x	xx.x, xx.x
	Full IHV01/A244 + ALFQ	x	xx.x	xx.x	xx.x	xx.x, xx.x
	Fractional IHV01/A244 + ALFQ	x	xx.x	xx.x	xx.x	xx.x, xx.x
	Placebo	x	xx.x	xx.x	xx.x	xx.x, xx.x
Note: N = Number of participants in the Safety Population with results available						

IMMUNOGENICITY**Table 29: Durability of Response as Measured by Area Under the Response Curve, by Antigen and Vaccination Group – [Assay name]**

Antigen	Full IHV01/A244 (N=X)		Fractional IHV01/A244 (N=X)		Full IHV01/A244 + ALFQ (N=X)		Fractional IHV01/A244 + ALFQ (N=X)		Placebo (N=X)		p- value ^a
	n	Mean (95% CI)	n	Mean (95% CI)	n	Mean (95% CI)	n	Mean (95% CI)	n	Mean (95% CI)	
gp120 A244gD-D11	xx	xx.x (xx.x, xx.x)	xx	xx.x (xx.x, xx.x)	xx	xx.x (xx.x, xx.x)	xx	xx.x (xx.x, xx.x)	xx	xx.x (xx.x, xx.x)	0.xx
gp120 MNgD- D11	xx	xx.x (xx.x, xx.x)	xx	xx.x (xx.x, xx.x)	xx	xx.x (xx.x, xx.x)	xx	xx.x (xx.x, xx.x)	xx	xx.x (xx.x, xx.x)	0.xx
gp70V1V2 92TH023	xx	xx.x (xx.x, xx.x)	xx	xx.x (xx.x, xx.x)	xx	xx.x (xx.x, xx.x)	xx	xx.x (xx.x, xx.x)	xx	xx.x (xx.x, xx.x)	0.xx
gp70V1V2 Case A2	xx	xx.x (xx.x, xx.x)	xx	xx.x (xx.x, xx.x)	xx	xx.x (xx.x, xx.x)	xx	xx.x (xx.x, xx.x)	xx	xx.x (xx.x, xx.x)	0.xx
[Additional antigens]											

Note: N = Number of participants in the Immunogenicity Population; n = Number of participants with available analysis values

^aANOVA used to compare mean log AUC across all vaccination groups

Table 30: Pairwise Comparisons of Log AUC Between Vaccination Groups by Antigen – [Assay name]

Antigen	Comparison	p-value ^a	Adjusted p-value ^b
gp120A244gD-D11	Full IHV01/A244 vs. Placebo	0.xx	0.xx
	Fractional IHV01/A244 vs. Placebo	0.xx	0.xx
	Full IHV01/A244 + ALFQ vs. Placebo	0.xx	0.xx
	Fractional IHV01/A244 + ALFQ vs. Placebo	0.xx	0.xx
	Full IHV01/A244 vs. Fractional IHV01/A244	0.xx	0.xx
	Full IHV01/A244 vs. Full IHV01/A244 + ALFQ	0.xx	0.xx
	Full IHV01/A244 vs. Fractional IHV01/A244 + ALFQ	0.xx	0.xx
	[Additional pairwise comparisons]	0.xx	0.xx
[Additional antigens]			

^aTwo-sided t-test used to compare log AUC group means
^bStep-down Bonferroni-Holm procedure used

Table 31: Collapsed Comparisons of Log AUC by Antigen – [Assay name]

Antigen	Full IHV01/A244 (N=X)		Fractional IHV01/A244 (N=X)		p-value ^a	ALFQ (N=X)		No ALFQ (N=X)		p-value ^a
	n	Mean (95% CI)	n	Mean (95% CI)		n	Mean (95% CI)	n	Mean (95% CI)	
gp120A244gD-D11	xx	xx.x (xx.x, xx.x)	xx	xx.x (xx.x, xx.x)	0.xx	xx	xx.x (xx.x, xx.x)	xx	xx.x (xx.x, xx.x)	0.xx
[Additional antigens]										

Note: N = Number of participants in the Immunogenicity Population; n = Number of participants with available analysis values

^aTwo-sided t-tests used

Table 32: Geometric Mean Titers and Associated 95% CIs by Visit, Antigen, and Vaccination Group – [assay name]

Visit	Antigen	Full IHV01/A244 (N=X)		Fractional IHV01/A244 (N=X)		Full IHV01/A244 + ALFQ (N=X)		Fractional IHV01/A244 + ALFQ (N=X)		Placebo (N=X)		p-value ^a
		n	GMT (95% CI)	n	GMT (95% CI)	n	GMT (95% CI)	n	GMT (95% CI)	n	GMT (95% CI)	
Baseline (Day 0)	gp120A244gD-D11	xx	xx.x (xx.x, xx.x)	xx	xx.x (xx.x, xx.x)	xx	xx.x (xx.x, xx.x)	xx	xx.x (xx.x, xx.x)	xx	xx.x (xx.x, xx.x)	0.xx
	[Additional antigens]	xx	xx.x (xx.x, xx.x)	xx	xx.x (xx.x, xx.x)	xx	xx.x (xx.x, xx.x)	xx	xx.x (xx.x, xx.x)	xx	xx.x (xx.x, xx.x)	0.xx
		xx	xx.x (xx.x, xx.x)	xx	xx.x (xx.x, xx.x)	xx	xx.x (xx.x, xx.x)	xx	xx.x (xx.x, xx.x)	xx	xx.x (xx.x, xx.x)	0.xx
[Additional visits or Peak]		xx	xx.x (xx.x, xx.x)	xx	xx.x (xx.x, xx.x)	xx	xx.x (xx.x, xx.x)	xx	xx.x (xx.x, xx.x)	xx	xx.x (xx.x, xx.x)	0.xx

Note: N = Number of participants in the Immunogenicity Population; n = Number of participants with available samples
^aANOVA used to compare log titer group means across all vaccination groups

Note: This will be adapted for assays with continuous analysis values, as appropriate

Table 33: Pairwise Comparisons of Geometric Mean Titers Between Vaccination Groups, by Visit and Antigen – [Assay name]

Visit	Antigen	Comparison	p-value ^a	Adjusted p-value ^b
Visit 2 (Day 1)	gp120A244gD-D11	Full IHV01/A244 vs. Placebo	0.xx	0.xx
		Fractional IHV01/A244 vs. Placebo	0.xx	0.xx
		Full IHV01/A244 + ALFQ vs. Placebo	0.xx	0.xx
		Fractional IHV01/A244 + ALFQ vs. Placebo	0.xx	0.xx
		Full IHV01/A244 vs. Fractional IHV01/A244	0.xx	0.xx
		Full IHV01/A244 vs. Full IHV01/A244 + ALFQ	0.xx	0.xx
		Full IHV01/A244 vs. Fractional IHV01/A244 + ALFQ	0.xx	0.xx
		[Additional pairwise comparisons]	0.xx	0.xx
	[Additional antigens]			
[Additional visits or Peak]				

^aTwo-sided t-test used to compare log titer group means^bStep-down Bonferroni-Holm procedure used

Table 34: Collapsed Comparisons of Geometric Mean Titers, by Visit and Antigen – [Assay name]

Visit	Antigen	Full IHV01/A244 (N=X)		Fractional IHV01/A244 (N=X)		p-value ^a	ALFQ (N=X)		No ALFQ (N=X)		p-value ^a
		n	GMT (95% CI)	n	GMT (95% CI)		n	GMT (95% CI)	n	GMT (95% CI)	
Visit 2 (Day 1)	gp120A244gD-D11	xx	xx.x (xx.x, xx.x)	xx	xx.x (xx.x, xx.x)	0.xx	xx	xx.x (xx.x, xx.x)	xx	xx.x (xx.x, xx.x)	0.xx
	[Additional antigens]										
[Additional visits or Peak]											

Note: N = Number of participants in the Immunogenicity Population; n = Number of participants with available samples

^aTwo-sided t-tests used

Table 35: GEE Model to Evaluate the Longitudinal Immune Response and Relationship with Vaccine Dosage and Adjuvant – [Assay name]

Model Parameter	Value	Parameter Estimate	SE	p-value
Intercept	Intercept	XXX.X	XXX.X	X.XXX
Vaccine Dosage	Fractional Dose (reference)			
	Full Dose	XXX.X	XXX.X	X.XXX
Adjuvant	None (Reference)			
	ALFQ	XXX.X	XXX.X	X.XXX
Study Day	Day 0 (Reference)			
	Day 14	XXX.X	XXX.X	X.XXX
	Day 168	XXX.X	XXX.X	X.XXX
	Day 336	XXX.X	XXX.X	X.XXX
Dosage*Adjuvant Interaction	[All interaction levels]	XXX.X	XXX.X	X.XXX
		XXX.X	XXX.X	X.XXX
Dosage*Study Day Interaction	[All interaction levels]	XXX.X	XXX.X	X.XXX
Adjuvant*Study Day Interaction	[All interaction levels]	XXX.X	XXX.X	X.XXX
Dosage*Adjuvant*Study Day Interaction	[All interaction levels]	XXX.X	XXX.X	X.XXX
Note: N=[XXX] participants in the Immunogenicity Population with results available for at least one post vaccination visit included in the GEE model.				

Table 36: Linear Regression Model to Evaluate the Relationship Between the Immune Response and Potential Confounders– [Assay name]

Model Parameter	Value	Parameter Estimate	SE	p-value
Intercept	Intercept	xxx.x	xxx.x	x.XXX
Biological Sex	Male (Reference)			
	Female	xxx.x	xxx.x	x.XXX
Time from Final RV306 Dose to RV546 Dose	Years (Continuous)	xxx.x	xxx.x	x.XXX
RV306 Vaccination Group	Group 2 (Reference)			
	Group 3	xxx.x	xxx.x	x.XXX
	Group 4A	xxx.x	xxx.x	x.XXX
	Group 4B	xxx.x	xxx.x	x.XXX
Vaccination Group	Placebo (Reference)			
	Fractional IHV01/A244	xxx.x	xxx.x	x.XXX
	Full IHV01/A244	xxx.x	xxx.x	x.XXX
	Fractional IHV01/A244 + ALFQ	xxx.x	xxx.x	x.XXX
	Full IHV01/A244 + ALFQ	xxx.x	xxx.x	x.XXX
Note: N=[XXX] participants in the Immunogenicity Population with results available included in the model.				

Table 37: Seroconversion Percentages by Visit, Antigen, and Vaccination Group – [Assay name]

Visit	Antigen	Full IHV01/A244 (N=X)		Fractional IHV01/A244 (N=X)		Full IHV01/A244 + ALFQ (N=X)		Fractional IHV01/A244 + ALFQ (N=X)		Placebo (N=X)		p-value ^a
		n	Estimate (95% CI)	n	Estimate (95% CI)	n	Estimate (95% CI)	n	Estimate (95% CI)	n	Estimate (95% CI)	
Visit 2 (Day 1)	gp120A244gD- D11	xx	xx.x (xx.x, xx.x)	xx	xx.x (xx.x, xx.x)	xx	xx.x (xx.x, xx.x)	xx	xx.x (xx.x, xx.x)	xx	xx.x (xx.x, xx.x)	0.xx
	[Additional antigens]	xx	xx.x (xx.x, xx.x)	xx	xx.x (xx.x, xx.x)	xx	xx.x (xx.x, xx.x)	xx	xx.x (xx.x, xx.x)	xx	xx.x (xx.x, xx.x)	0.xx
[Additional visits]		xx	xx.x (xx.x, xx.x)	xx	xx.x (xx.x, xx.x)	xx	xx.x (xx.x, xx.x)	xx	xx.x (xx.x, xx.x)	xx	xx.x (xx.x, xx.x)	0.xx
		xx	xx.x (xx.x, xx.x)	xx	xx.x (xx.x, xx.x)	xx	xx.x (xx.x, xx.x)	xx	xx.x (xx.x, xx.x)	xx	xx.x (xx.x, xx.x)	0.xx

Note: N = Number of participants in the Immunogenicity Population; n = Number of participants with available samples

^aExact binomial tests used to compare proportions across all vaccination groups

Table 38: Pairwise Comparisons of Seroconversion Percentages Between Vaccination Groups, by Visit and Antigen – [Assay name]

Visit	Antigen	Comparison	p-value ^a	Adjusted p-value ^b
Baseline (Day 1)	gp120A244gD-D11	Full IHV01/A244 vs. Placebo	0.xx	0.xx
		Fractional IHV01/A244 vs. Placebo	0.xx	0.xx
		Full IHV01/A244 + ALFQ vs. Placebo	0.xx	0.xx
		Fractional IHV01/A244 + ALFQ vs. Placebo	0.xx	0.xx
		Full IHV01/A244 vs. Fractional IHV01/A244	0.xx	0.xx
		Full IHV01/A244 vs. Full IHV01/A244 + ALFQ	0.xx	0.xx
		Full IHV01/A244 vs. Fractional IHV01/A244 + ALFQ	0.xx	0.xx
		[Additional pairwise comparisons]	0.xx	0.xx
	[Additional antigens]			
[Additional visits]				

^aExact binomial test used to compare seroconversion^bStep-down Bonferroni-Holm procedure used

Table 39: Collapsed Comparisons of Seroconversion Percentages, by Visit and Antigen – [Assay name]

Visit	Antigen	Full IHV01/A244 (N=X)		Fractional IHV01/A244 (N=X)		p-value ^a	ALFQ (N=X)		No ALFQ (N=X)		p-value ^a
		n	Seroconversion % (95% CI)	n	Seroconversion % (95% CI)		n	Seroconversion % (95% CI)	n	Seroconversion % (95% CI)	
Visit 2 (Day 1)	gp120A244gD-D11	xx	xx.x (xx.x, xx.x)	xx	xx.x (xx.x, xx.x)	0.xx	xx	xx.x (xx.x, xx.x)	xx	xx.x (xx.x, xx.x)	0.xx
	[Additional antigens]										
[Additional visits]											

Note: N = Number of participants in the Immunogenicity Population; n = Number of participants with available samples

^a Exact binomial tests used

Table 40: Summary of Peak Week of Response, by Antigen and Vaccination Group – [Assay name]

Vaccination Group	N	Mean	Standard Deviation	Median	Min, Max
Full IHV01/A244	x	xx.x	xx.x	xx.x	xx.x, xx.x
Fractional IHV01/A244	x	xx.x	xx.x	xx.x	xx.x, xx.x
Full IHV01/A244 + ALFQ	x	xx.x	xx.x	xx.x	xx.x, xx.x
Fractional IHV01/A244 + ALFQ	x	xx.x	xx.x	xx.x	xx.x, xx.x
Placebo	x	xx.x	xx.x	xx.x	xx.x, xx.x

[figure not shown]
Note: N = Number of participants in the Immunogenicity Population

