11.3.1. Severity Assessment

All AEs will be assessed for severity by the investigator. Inherent in this assessment is the medical and clinical consideration of all information surrounding the event including any medical intervention required. Each event will be assigned one of the following categories: mild, moderate, severe, or potentially life-threatening. Refer to the DAIDS grading scale in [Appendix B](#) for further guidance in the assignment of severity. The criteria below may be used for any symptom not included in the grading scale. Any grade 4 (potentially life-threatening) or grade 5 (death) AE must be reported as an SAE.

The severity reported on the AEs form will reflect only the highest severity for continuous days an event occurred.

Mild (Grade 1): Does not interfere with routine activities; minimal level of discomfort.

Moderate (Grade 2): Interferes with routine activities; moderate level of discomfort.

Severe (Grade 3): Unable to perform routine activities; significant level of discomfort.

Potentially life-threatening (Grade 4): Hospitalization, ER visit, or urgent intervention indicated for potentially life-threatening event.

Death (Grade 5): Death.

As defined by the ICH guideline for GCP, the term “severe” is often used to describe intensity (severity) of a specific event (as in mild, moderate, or severe myocardial infarction); the event itself however, may be of relatively minor medical significance (such as severe headache). This is **not** the same as “serious”, which is based on participant/event **outcome** or **action** criteria usually associated with events that pose a threat to a participant’s life or functioning. Seriousness (not severity) serves as a guide for defining regulatory reporting obligations.

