4. INVESTIGATIONAL PLAN

4.1. Overall Study Design and Plan

This is a Phase I randomized, double-blind, placebo-controlled clinical trial to define the safety and immunogenicity of IHV01/A244 with and without ALFQ at a full dose and at a fractional dose in a late boost setting for participants who had previously received the AIDSVAX®B/E with or without ALVAC in RV306. Participants will be randomized to receive 2 intramuscular (IM) injections, either IHV01/A244 (target of n=64 total, with n=16 per study arm) or saline placebo (target of n=16 total, with n=4 per study arm), into the same quadriceps muscle at Day 0. Half of the IHV01/A244 recipients will receive the full IHV01 (FLSC) dose (Groups 1 and 3) while the other half (Groups 2 and 4) will receive a fractional dose of each vaccine, which is one fifth of the standard dose. Groups 3 and 4 will also receive ALFQ. Enrollment will be sequential, with Groups 1 and 2 accruing first with a 2:2:1 ratio of full dose to fractional dose to placebo, followed by enrollment into Groups 3 and 4 with the same targeted allocation ratios. After the first 8 participants are enrolled across Groups 1 and 2, the Safety Monitoring Committee (SMC) will review 7 days of safety data from these participants to determine whether enrollment can continue. Enrollment into Groups 1 and 2 will continue unrestricted after any safety concerns raised by the SMC are addressed and the Sponsor gives their approval for the continuation of enrollment. Enrollment into Groups 3 and 4 will commence after enrollment into Groups 1 and 2 has been completed, the SMC has reviewed 7 days of safety data from all Group 1 and Group 2 participants, and the Sponsor gives their approval. Enrollment into Groups 3 and 4 will follow a similar approach with an SMC review of 7 days of safety data from the first 8 participants enrolled across both groups, and Sponsor approval before enrollment can continue unrestricted in Groups 3 and 4.

Participants will receive 2 IM injections, either IHV01/A244 (n=64) or saline placebo (n=16) at Day 0, and return for follow up at 1, 7, 14, 168, and 336 days after vaccination (protocol version 5.0, section 7.2). Figure 1 gives a schematic of the study design, with the RV306 groups shown on the left and the RV546 groups on the right.

Figure 1: Study Schematic

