5.8. Multiple Comparisons/Multiplicity

For comparisons of safety outcomes, 5%-level two-sided tests will be made. Some of these may be implicit comparisons based on the overlap of group-level confidence intervals (i.e. non-overlapping 95% CIs mean rejecting the null hypothesis of no difference between groups at the 0.05-level).

To compare primary immunogenicity outcomes (antigen-specific plasma IgG binding responses, as measured by log AUC over time) across all groups, 5%-level two-sided tests will be used. When differences are found, pairwise comparisons between vaccination groups will be made using the Bonferroni-Holm step-down procedure [1] and a 5% significance threshold for the adjusted p-values; if no difference is found across all groups, no pairwise comparisons will be made. Collapsed comparisons will be considered separately and will be made with 2.5%-level two-sided tests, even when no pairwise differences are observed.

Further exploratory comparisons for immunogenicity endpoints across all groups will be adjusted for multiplicity by a Bonferroni adjustment: multiplying p-values by the number of assays in the same set (e.g. across antigens for a given antibody test; see Section 3.2.2 for sets of assays). Then a similar process as above will be followed, with pairwise comparisons following a significant overall test and Bonferroni-Holm step-down procedure (with a 5% significance level) to account for the multiple pairwise tests.

These adjustments are intended to improve control of the type-I error across comparisons for the same outcome measure and time point (e.g. Geometric Mean Titers (GMTs) for gp120A244 plasma IgG binding at Day 14) rather than across outcome measures and/or time. This level of type-I error control will still allow for exploratory findings that would be assessed further in future studies.

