7.1. Primary Safety Analysis

7.1.1. Unsolicited Adverse Events

Unsolicited AEs will be listed and summarized by MedDRA system order class (SOC) and preferred term (PT) for each vaccination group. These will be described overall and within 28 days post-vaccination. A participant will be counted only once per PT per reporting period. SAEs, unexpected AEs, and AESIs will be summarized and listed. The number and percentage of participants reporting each PT, along with the associated 95% exact Clopper-Pearson CI for the underlying probability of the event, will be presented.

The likelihood of reporting AEs, SAEs, and AESIs will be compared between collapsed groups (Groups 1+2 vs. Groups 3+4 to assess ALFQ safety, Groups 1+3 vs. Groups 2+4 to assess vaccine dose) via exact binomial tests. If computational challenges arise, Chi-squared tests may be used instead. Calculated confidence intervals will be used to compare pairs of individual vaccination groups, instead of formal hypothesis testing; when CIs for the same event in two groups do not overlap, this corresponds to a p-value of less than 0.05 for the analogous exact binomial test.

Unsolicited AEs will also be tabulated by investigator-determined relationship to investigational product and severity for each vaccination group.

Incident HIV infections, as diagnosed by the algorithm in Section 11.1.4.4 of the protocol, will be presented in a listing.

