^b See listing of Serious Adverse Events												

Table 14: Adverse Events Occurring in 5% of Participants in Any Vaccination Group by MedDRA System Organ Class and Preferred Term, and Vaccination Group

MedDRA System Organ Class	MedDRA Preferred Term	Full IHV01/A244 (N=X)			Fractional IHV01/A244 (N=X)			Full IHV01/A244 + ALFQ (N=X)			Fractional IHV01/A244 + ALFQ (N=X)			Placebo (N=X)			All Participants (N=X)		
		n	%	Events	n	%	Events	n	%	Events	n	%	Events	n	%	Events	n	%	Events
Serious Adverse Events																			
All	All	x	x.x	x	x	x.x	x	x	x.x	x	x	x.x	x	x	x.x	x	x	x.x	x
SOC1	PT1	x	x.x	x	x	x.x	x	x	x.x	x	x	x.x	x	x	x.x	x	x	x.x	x
Etc.	Etc.																		
Other (Non-Serious) Adverse Events																			
All	All	x	x.x	x	x	x.x	x	x	x.x	x	x	x.x	x	x	x.x	x	x	x.x	x
SOC1	PT1	x	x.x	x	x	x.x	x	x	x.x	x	x	x.x	x	x	x.x	x	x	x.x	x
Etc	Etc																		
Solicited Adverse Events																			
All	All	x	x.x	x	x	x.x	x	x	x.x	x	x	x.x	x	x	x.x	x	x	x.x	x
SOC1	PT1	x	x.x	x	x	x.x	x	x	x.x	x	x	x.x	x	x	x.x	x	x	x.x	x
Etc	Etc																		
Clinical Laboratory Adverse Events																			
All	All	x	x.x	x	x	x.x	x	x	x.x	x	x	x.x	x	x	x.x	x	x	x.x	x
SOC1	PT1	x	x.x	x	x	x.x	x	x	x.x	x	x	x.x	x	x	x.x	x	x	x.x	x
Etc	Etc																		
Note: N = Number of participants in the Safety Population; n = Number of participants reporting event; Events = Total frequency of events reported.																			

Table 15: Collapsed Comparisons of the Proportion of Participants Experiencing Adverse Events by Event Type

Event Type	Full IHV01/A244 (N=X)	Fractional IHV01/A244 (N=X)	p-value ^a	Any ALFQ (N=X)	No ALFQ (N=X)	p-value ^a
	n (%)	n (%)		n (%)	n (%)	
Solicited Adverse Events						
Any Solicited Symptom	x (x.x)	x (x.x)	0.xx	x (x.x)	x (x.x)	0.xx
Moderate (Grade 2) ^b	x (x.x)	x (x.x)	0.xx	x (x.x)	x (x.x)	0.xx
Severe (Grade 3) ^b	x (x.x)	x (x.x)	0.xx	x (x.x)	x (x.x)	0.xx
Any Systemic Symptom	x (x.x)	x (x.x)	0.xx	x (x.x)	x (x.x)	0.xx
Moderate (Grade 2) ^b	x (x.x)	x (x.x)	0.xx	x (x.x)	x (x.x)	0.xx
Severe (Grade 3) ^b	x (x.x)	x (x.x)	0.xx	x (x.x)	x (x.x)	0.xx
Any Local Symptom	x (x.x)	x (x.x)	0.xx	x (x.x)	x (x.x)	0.xx
Moderate (Grade 2) ^b	x (x.x)	x (x.x)	0.xx	x (x.x)	x (x.x)	0.xx
Severe (Grade 3) ^b	x (x.x)	x (x.x)	0.xx	x (x.x)	x (x.x)	0.xx
Unsolicited Adverse Events						
Any Serious Adverse Event	x (x.x)	x (x.x)	0.xx	x (x.x)	x (x.x)	0.xx
Any Adverse Event of Special Interest	x (x.x)	x (x.x)	0.xx	x (x.x)	x (x.x)	0.xx

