Any Related, Unexpected Adverse Event	x (x.x)	x (x.x)	0.xx	x (x.x)	x (x.x)	0.xx
Any Unexpected Adverse Event Within 28 Days of Study Vaccination	x (x.x)	x (x.x)	0.xx	x (x.x)	x (x.x)	0.xx
Note: N = Number of participants in the Safety Population; n = Number of participants reporting each symptom						
^a Exact binomial tests used						
^b Maximum severity reported						

SOLICITED ADVERSE EVENTS

Table 16: Number and Percentage of Participants Experiencing Solicited Reactogenicity Events with 95% Confidence Intervals, by Event and Vaccination Group

Event	Full IHV01/A244 (N=X)			Fractional IHV01/A244 (N=X)			Full IHV01/A244 + ALFQ (N=X)			Fractional IHV01/A244 + ALFQ (N=X)			Placebo (N=X)			All Participants (N = X)		
	n	%	95% CI	n	%	95% CI	n	%	95% CI	n	%	95% CI	n	%	95% CI	n	%	95% CI
Any Reactogenicity	x	x.x	x.x, x.x	x	x.x	x.x, x.x	x	x.x	x.x, x.x	x	x.x	x.x, x.x	x	x.x	x.x, x.x	x	x.x	x.x, x.x
Any Systemic Reactogenicity	x	x.x	x.x, x.x	x	x.x	x.x, x.x	x	x.x	x.x, x.x	x	x.x	x.x, x.x	x	x.x	x.x, x.x	x	x.x	x.x, x.x
[Systemic Event 1]	x	x.x	x.x, x.x	x	x.x	x.x, x.x	x	x.x	x.x, x.x	x	x.x	x.x, x.x	x	x.x	x.x, x.x	x	x.x	x.x, x.x
[Systemic Event 2]	x	x.x	x.x, x.x	x	x.x	x.x, x.x	x	x.x	x.x, x.x	x	x.x	x.x, x.x	x	x.x	x.x, x.x	x	x.x	x.x, x.x
Any Local Reactogenicity	x	x.x	x.x, x.x	x	x.x	x.x, x.x	x	x.x	x.x, x.x	x	x.x	x.x, x.x	x	x.x	x.x, x.x	x	x.x	x.x, x.x
[Local Event 1]	x	x.x	x.x, x.x	x	x.x	x.x, x.x	x	x.x	x.x, x.x	x	x.x	x.x, x.x	x	x.x	x.x, x.x	x	x.x	x.x, x.x
[Local Event 2]	x	x.x	x.x, x.x	x	x.x	x.x, x.x	x	x.x	x.x, x.x	x	x.x	x.x, x.x	x	x.x	x.x, x.x	x	x.x	x.x, x.x
Note: N = Number of participants in the Safety Population																		

Tables with similar format:

Table 17: Number and Percentage of Male Participants Experiencing Solicited Reactogenicity Events with 95% Confidence Intervals, by Event and Vaccination Group

Table 18: Number and Percentage of Female Participants Experiencing Solicited Reactogenicity Events with 95% Confidence Intervals, by Event and Vaccination Group

Table 19: Number and Percentage of Participants Experiencing Solicited Reactogenicity Events by Event, Maximum Severity, and Vaccination Group

Event	Severity	Full IHV01/A244 (N=X)		Fractional IHV01/A244 (N=X)		Full IHV01/A244 + ALFQ (N=X)		Fractional IHV01/A244 + ALFQ (N=X)		Placebo (N=X)	
		n	%	n	%	n	%	n	%	n	%
Any Reactogenicity	None	X	X.X	X	X.X	X	X.X	X	X.X	X	X.X
	Mild	X	X.X	X	X.X	X	X.X	X	X.X	X	X.X
	Moderate	X	X.X	X	X.X	X	X.X	X	X.X	X	X.X
	Severe	X	X.X	X	X.X	X	X.X	X	X.X	X	X.X

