MedDRA® System Organ Class	MedDRA® Preferred Term	Any Incidence		Severity ¹				Relationship to Treatment ²					
				Mild		Moderate		Severe		Not Related		Related	
		n	%	n	%	n	%	n	%	n	%	n	%
Full IHV01/A244 (N=X)													
Any SOC	Any PT	x	xx	x	xx	x	xx	x	xx	x	xx	x	xx
[SOC 1]	Any PT												
	[PT 1]												
	[PT 2]												
[SOC 2]	Any PT												
	[PT 1]												
	[PT 2]												
Fractional IHV01/A244 (N=X)													
[repeat for all groups]													
Note: N = Number of participants in the Safety Population.													
¹ For severity, a participant is counted once per preferred term and is summarized according to the highest reported severity.													
² For relationship, a participant is only counted once per preferred term and is summarized according to the closest reported relationship.													

Table 26: Number and Percentage of Participants Experiencing Unsolicited Adverse Events Within 28 Days of Study Vaccination, by MedDRA® System Organ Class and Preferred Term, Maximum Severity, Relationship, and Vaccination Group

MedDRA® System Organ Class	MedDRA® Preferred Term	Any Incidence	Severity ¹				Relationship to Treatment ²							
			Mild		Moderate		Severe		Not Related		Related			
			n	%	n	%	n	%	n	%	n	%	n	%
Full IHV01/A244 (N=X)														
Any SOC	Any PT		x	xx	x	xx	x	xx	x	xx	x	xx	x	xx
[SOC 1]	Any PT													
	[PT 1]													
	[PT 2]													
[SOC 2]	Any PT													
	[PT 1]													
	[PT 2]													
Fractional IHV01/A244 (N=X)														
[repeat for all groups]														
Note: N = Number of participants in the Safety Population.														
¹ For severity, a participant is counted once per preferred term and is summarized according to the highest reported severity.														
² For relationship, a participant is only counted once per preferred term and is summarized according to the closest reported relationship.														

Table 27: Summary of Laboratory Results by Parameter, Maximum Severity, Visit, and Vaccination Group – [Parameter]

Visit	Vaccination Group	N	None		Mild / Grade 1		Moderate/ Grade 2		Severe/ Grade 3		Missing	
			n	%	n	%	n	%	n	%	n	%
Baseline (Day 0)	Full IHV01/A244	x	x	x.x	x	x.x	x	x.x	x	x.x	x	x.x
	Fractional IHV01/A244	x	x	x.x	x	x.x	x	x.x	x	x.x	x	x.x
	Full IHV01/A244 + ALFQ	x	x	x.x	x	x.x	x	x.x	x	x.x	x	x.x
	Fractional IHV01/A244 + ALFQ	x	x	x.x	x	x.x	x	x.x	x	x.x	x	x.x
	Placebo	x	x	x.x	x	x.x	x	x.x	x	x.x	x	x.x

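### SAP Table 15 tests Grade 2 and Grade 3 solicited reactions as separate maximum-severity bands, so a severity shift under ALFQ is diluted across rows; cumulative rows would avoid this at no cost

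*SAP*

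**What the plan says.** SAP Table 15 (Appendix 1) has three solicited blocks: any, systemic and local symptoms. Each block has an Any row, a row that begins "Moderate (Grade 2" and a Grade 3 row. Every row carries one p-value for full versus fractional dose and one for any versus no ALFQ. The footnote attached only to the graded rows is "Maximum severity reported". The test footnote is "Exact binomial tests used".

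SAP 7.1.1 defines the adjuvant contrast as "Groups 1+2 vs. Groups 3+4 to assess ALFQ safety", and SAP 7.1.2 carries the collapsed comparisons over to solicited events. Neither section adds a test of a grade or higher, or an ordinal test. SAP 5.8 sets the level: "For comparisons of safety outcomes, 5%-level two-sided tests will be made".

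Protocol 11.3.1 grades events up to 5 and adds: "Any grade 4 (potentially life-threatening) or grade 5 (death) AE must be reported as an SAE". In SAP Tables 13, 19, 25 and 26 the severity levels stop at severe. In Table 27, the laboratory table, the last graded column is "Severe/ Grade 3", followed only by a missing column.

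**The concern.** Safety is the primary objective, and Protocol 12.2.3 names with versus without ALFQ as a key comparison. Protocol 5.5.3 reports that local pain and tenderness were near-universal in earlier ALFQ studies. The Any Local row may therefore be close to saturated in the ALFQ groups, and severity may carry much of the information.

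With mutually exclusive bands, the two graded rows work against each other. An adjuvant that pushes some participants from Grade 1 to 2 and others from Grade 2 to 3 adds to the Grade 2 row and takes from it at the same time. That row can show little or no difference when severity has clearly risen. A participant whose maximum is Grade 4 contributes to neither graded test. Whether ALFQ raises the proportion with a moderate or worse reaction is never tested directly.

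**Working it through.** **Inputs.**
- Group size: "target of n=64 total, with n=16 per study arm" (SAP 4.1), so each collapsed group has 16 + 16 = 32.
- Level: two-sided 5% (SAP 5.8).
- Test: the SAP says exact binomial without naming a two-sample version; Fisher's exact test is used here.
- Grade distributions: **assumed**, because the documents give none.

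**The plan's own figures first.** The documents state no power for any Table 15 row. The nearest figure is the upper exact 95% limit with zero events, 1 − 0.025^(1/n). For n = 16 this is 20.6%, and for n = 32 it is 10.9%. Both match SAP Table 3.

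**Illustrative counts, 32 versus 32 (no ALFQ versus ALFQ).**
1. Grade 2 in 5 versus 9: p = 0.36. Grade 3 in 0 versus 5: p = 0.053. Grade 2 or higher is 5 + 0 = 5 versus 9 + 5 = 14: p = 0.027. Both planned graded rows miss 5%; the cumulative row does not.
2. Maximum grades 0 to 4 of 4/17/10/1/0 versus 1/10/10/8/3. Grade 2 alone is 10 versus 10, p = 1.000. Grade 2 or higher is 10 + 1 + 0 = 11 versus 10 + 8 + 3 = 21, p = 0.024. Here the Grade 3 row does detect the shift (1 versus 8, p = 0.026), but it omits three Grade 4 participants; with them it is 1 versus 11, p = 0.003.
3. One Grade 4 participant can matter at the margin. Five Grade 3 participants against none gives p = 0.053; adding one Grade 4 participant makes it 0 versus 6, p = 0.024.

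**Power.** For true proportions p₀ and p₁, power = Σₐ Σ_b Bin(a; 32, p₀) · Bin(b; 32, p₁) · 1[Fisher p(a, b) ≤ 0.05]. Hold Grade 2 or higher at 20% versus 55% and change only how much of it is Grade 3 (no Grade 4). The Grade 2 band is what remains.

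| Grade 3 (no ALFQ vs ALFQ) | Grade 2 band | Power, Grade 2 row | Power, Grade 3 row | Power, Grade 2 or higher | Loss in Grade 2 row |
|---|---|---|---|---|---|
| 1% vs 3% | 19% vs 52% | 73.7% | <0.1% | 78.3% | 4.6 points |
| 1% vs 5% | 19% vs 50% | 68.0% | 0.3% | 78.3% | 10.3 points |
| 2% vs 7% | 18% vs 48% | 65.9% | 1.2% | 78.3% | 12.4 points |
| 3% vs 15% | 17% vs 40% | 44.5% | 17.4% | 78.3% | 33.8 points |

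In the last line, counting a rejection in either graded row gives 57%, still below 78%.

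**The other tables.** Tables 13, 19 and 25–27 contain no tests, so the power argument does not reach them. In Tables 25 and 26 a Grade 4 participant is counted under Any Incidence but has no severity column. Table 27 allows None, Grades 1 to 3 and Missing, so a Grade 4 laboratory value has no column at all.

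**The case against.** The case for leaving the table alone has several parts.

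- **Grade 4 events are covered elsewhere.** A reader might infer that they vanish from the report. The documents do not support that. Protocol 11.3.1 makes every Grade 4 event a serious adverse event. Such events are counted in Table 13, tested in Table 15 and listed with severity in Listing 9, and a Grade 4 solicited reaction stays in the Any rows. This stands, with two limits. Table 15's serious-event row sits under the unsolicited heading and mixes causes, so it does not test reactogenicity. Under SAP 7.1.3, laboratory values become adverse events only if clinically significant, so a Grade 4 value not judged so would appear only in Listing 11.
- **Counts can be added.** If the bands are exclusive, a reader can sum the two printed counts and add any listed Grade 4. True; what is missing is the planned test. Table 19 and Figures 3 and 4 show maximum severity by individual group, not for the pooled ALFQ contrast.
- **The large loss rests on a 15% Grade 3 rate.** Protocol 5.5.3 describes earlier ALFQ reactions as mild to moderate (systemic: mostly so) and names two severe cases. This stands: the rarer Grade 3 splits fit that description better, and the loss is then about 5 to 12 points.
- **The Grade 3 or higher row changes nothing unless a Grade 4 occurs.** Correct; without one, the gain is all in the Grade 2 row.
- **The study is descriptive.** Protocol 12.1 says so, and no power is claimed for these rows. But the SAP prints a p-value on each row, so how the row is defined still matters.

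**Conclusion.** The point holds as one of dilution. Reading the rows as single grades is an inference from their labels and the maximum-severity footnote, but it is the natural one, since no row says otherwise and Table 19 uses the same partition. Under that reading, a severity shift in the ALFQ contrast is spread over two competing tests, and Grade 4 enters neither.

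With 20% versus 55% at Grade 2 or worse and 32 per group, the Grade 2 row gives up about 5 to 12 points of power when Grade 3 is rare and about 34 when Grade 3 is 3% versus 15%. These figures rest on assumed grade distributions and on Fisher's test. A reader might conclude that the plan will miss an ALFQ effect on severity, or that 34 points is the expected loss. Neither follows: the Grade 3 row can detect a large enough shift, as the second example shows, and the larger figure needs more severe reactions than Protocol 5.5.3 suggests. For Tables 13, 19 and 25–27 the point is only a missing display level, and it matters most in Table 27.

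**What to change.** In SAP Table 15, replace the two graded rows in each solicited block with Grade 2 or higher and Grade 3 or higher, both by maximum severity and both including Grade 4. State the same definition in SAP 7.1.2. The count of graded tests stays at 3 blocks × 2 rows × 2 contrasts = 12.

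As a secondary display edit, label the top severity level in Tables 13, 19 and 25–27 as Grade 3 or higher, or add a Grade 4 level. Table 27 should come first.

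The cost is edits to table shells, one sentence of text and the matching programming. No new data, extra tests or changes to any clinical rule are needed.
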